5.8.1 Background medication

All patients will be maintained on androgen deprivation therapy (ADT) if they have not had a prior orchiectomy for the duration of the study. Patients may also be receiving osteoclast inhibitors for prevention of skeletal related events and these will be permitted to continue.

5.8.2 Other concomitant treatment

Other medication other than that described above, which is considered necessary for the patient's safety and wellbeing, may be given at the discretion of the Investigator and recorded in the appropriate sections of the Case Report Form.

In addition, any unplanned diagnostic, therapeutic or surgical procedure performed during the study period must be recorded in the CRF.

5.9 Dose modification

Dose Reductions

In case a dose reduction is necessary, the Study treatment will be administered as follows:

Table 6 Dose reductions for olaparib to manage adverse events

Initial Dose	Following re-challenge post interruption: Dose reduction 1	Dose reduction 2
300 mg twice daily	250 mg twice daily	200 mg twice daily

Table 7 Dose reduction for olaparib if patient develops moderate renal impairment

Initial Dose	Moderate renal impairment (calculated creatinine clearance by Cockcroft -Gault equation or based on a 24 hour urine test between 31 and 50 ml/min): Dose reduction
300 mg twice daily	200 mg twice daily

Table 8 Dose reductions for olaparib if patient has to start taking a strong or moderate CYP3A inhibitor

Initial Dose	Strong CYP3A inhibitor	Moderate CYP3A inhibitor
300 mg twice daily	100 mg twice daily	150 mg twice daily

For guidance on dose reductions for management of AEs (including renal impairment) refer to section 6.5.

For guidance on dose reductions when concomitant strong or moderate CYP3A inhibitors cannot be avoided see section 6.5.

When dose reduction is necessary patients will take one 150 mg tablet and one 100 mg tablet twice daily or two x 100 mg tablet twice daily (see Section 8.4.6), or one 150 mg tablet twice daily or one 100 mg tablet twice daily (see Section 6.5).

5.10 Treatment after the end of the study

Not applicable - please see Section 4.1 for details of treatment after the study database has been closed. discontinuation of treatment and patient withdrawal

5.11 Discontinuation of study treatment

Patients may be discontinued from investigational product (IP) in the following situations. Note that discontinuation from study treatment is NOT the same thing as a complete withdrawal from the study

- Patient decision. The patient is at any time free to discontinue treatment, without prejudice to further treatment
- Adverse Event
- Severe non-compliance with the Clinical Study Protocol
- Bone marrow findings consistent with myelodysplastic syndrome (MDS)/acute myeloid leukemia (AML)
- Subject is determined to have met one or more of the exclusion criteria for study participation at study entry and continuing investigational therapy might constitute a safety risk
- Study drug held for >4 weeks due to an AE

5.11.1 Procedures for discontinuation of study treatment

The investigator should instruct the patient to contact the site before or at the time if Study treatment is stopped. A patient that decides to discontinue Study treatment will always be asked about the reason(s) and the presence of any AEs. The date of last intake of Study treatment should be documented in the CRF (electronic or paper). All Study treatment should be returned by the patient at their next on-site study visit or unscheduled visit. Patients permanently discontinuing Study treatment should be given locally available standard of care therapy, at the discretion of the Investigator.

Any patient discontinuing investigational product should be seen post discontinuation for the evaluations and sample collections outlined in the study schedule.

After discontinuation of the study medication at any point in the study, all ongoing AEs or SAEs must be followed until resolution unless, in the Investigator's opinion the condition is unlikely to resolve due to the patients underlying disease, or the patient is lost to follow up (see Section 5.12) All new AEs and SAEs occurring during the 30 calendar days after the last dose of study medication must be reported (if SAEs, they must be reported within 24 hours as described in Section 6.4.2) and followed to resolution as above. Patients should be seen within 30 days after discontinuing study medication to collect and / or complete AE information. For guidance on reporting adverse events after the 30 day follow up period see Section 6.4.2.1.

Discontinuation of Study treatment, for any reason, does not impact on the patient's participation in the study. The patient should continue attending subsequent study visits and data collection should continue according to the study protocol. If the patient does not agree to continue in-person study visits, a modified follow-up must be arranged to ensure the collection of endpoints

and safety information. This could be a telephone contact with the patient, a contact with a relative or treating physician, or information from medical records. The approach taken should be recorded in the medical records. A patient that agrees to modified follow-up is not considered to have withdrawn consent or to have withdrawn from the study.

5.12 Lost to follow-up

Patients will be considered lost to follow-up only if no contact has been established by the time that the study is completed, such that there is insufficient information to determine the patient's status at that time. Patients who refuse to continue participation in the study, including telephone contact, should be documented as "withdrawal of consent" rather than "lost to follow-up." Treating physician and Sponsor Investigators should document attempts to re-establish contact with missing patients throughout the study period. If contact with a missing patient is re-established, the patient should not be considered lost to follow-up and evaluations should resume according to protocol.

In order to support key endpoints of PFS and OS analyses, the survival status of all patients in the full analysis and the safety analysis sets should be re-checked, this includes those patients who withdrew consent or are classified as "lost to follow up."

- Lost to Follow-up: site personnel should check hospital records, the patients' current physician, and a publicly available death registry to obtain a current survival status. (The applicable CRF modules will be updated).
- In the event that the patient has actively withdrawn consent to the processing of their personal data, the survival status of the patient can be obtained by site personnel from publicly available death registries where it is possible to do so under applicable local laws to obtain current survival status. (The applicable CRF modules will be updated).

5.13 Withdrawal from the study

Patients are free to withdraw from the study at any time without prejudice to further treatment. Patients who withdraw consent for further participation in the study will not receive any further olaparib or further study observation, with the exception of follow-up for survival, which will continue until the end of the study unless the patient has expressly withdrawn their consent to survival follow-up. Note that the patient may be offered additional tests or tapering of treatment to withdraw safely.

A patient who withdraws consent will always be asked about the reason(s) for withdrawal and the presence of any AE. The Sponsor Investigator will follow up AEs outside of the clinical study.

Biospecimens obtained, as part of trial participation will be retained.

6. STUDY ASSESSMENTS AND PROCEDURES

Assessments will be performed according to the Schedule of Activities (SoA).

6.1 Assessment of HRD

6.1.1 LOH Score

During pre-screening patients will be assessed for loss of heterozygosity (LOH) by the application of an LOH score that has been optimized for use on UW OncoPlex, a clinical grade sequencing assay. LOH events are detected using the R package Sequenza¹⁸, which uses data from tumor-normal sample pairs to probabilistically estimate tumor cellularity, ploidy, and allele-specific copy number abnormalities. Whole genome duplication or loss events, which arise from non-HRD associated mechanisms, are disqualified¹⁹. Using custom scripts, the LOH score is defined as the ratio of the genome affected by loss of heterozygosity events relative to the total number of sequenced nucleotides for which the tumor copy number state can be successfully inferred¹⁹.

6.1.2 iHRD Status

All patients will have iHRD status assessed during the screening phase by undergoing paired germline and somatic whole exome sequencing. iHRD is a genomic classification framework that incorporates LOH score, COSMIC Signature 3, COSMIC Signature 8, tumor ploidy, tumor purity and mutation burden to determine the classification status. The classification outcome is read as binary 1 and 0, equated to iHRD+ and iHRD- respectively.

6.2 Efficacy assessments

6.2.1 Primary Objective

The primary objective is to determine the percentage of men achieving at least a 50% decline in PSA (PSA50 response) after twelve weeks of treatment with Olaparib 300mg by mouth twice daily. PSA will be collected from peripheral blood every cycle during the treatment phase. The lowest on treatment PSA will be defined as the lowest value following at least 12 weeks of treatment (i.e. the beginning of Cycle 4).

6.2.2 Secondary and Exploratory Objectives

ORR and Radiographic Progression Free Survival

Radiographic assessments which include computed tomography scan of the chest, abdomen, and pelvis as well as a nuclear medicine bone scan will be conducted every 12 weeks (every 3 cycles) after screening. Radiographic response and progression will be defined per RECIST 1.1 criteria. RECIST 1.1 is an accepted methodology by regulatory authorities and will be used to assess tumor response in patients with soft tissue disease. For patients with bony disease, progression will be defined per PCWG3 criteria¹.

Exploratory Objectives

Correlative blood work and tissue analysis will be performed per the planned time points in the SoA. Full details of collection, processing, shipping, and storage of samples will be included in the Lab Manual.

6.3 Safety assessments

Planned time points for all safety assessments are provided in the SoA.

6.3.1 Clinical safety laboratory assessments

Blood samples for determination of clinical chemistry and hematology will be taken at the times indicated in the assessment schedules as clinically indicated (see the SoA). Clinical laboratory safety tests will be performed in a licensed clinical laboratory according to local standard procedures. Sample tubes and sample sizes may vary depending on the laboratory method used and routine practice at the site. Abnormal clinically significant laboratory results should be repeated as soon as possible (preferably within 24 to 48 hours).

Additional safety samples may be collected if clinically indicated at the discretion of the treating physician and sponsor investigator. The date, time of collection, and results (values, units, and reference ranges) will be recorded on the appropriate eCRF.

The laboratory variables to be measured are presented in this section in Table 9.

Table 9 Laboratory safety variables

Hematology/Hemostasis (whole blood)	Clinical Chemistry (serum or plasma)
B-Hemoglobin (Hb)	S/P-Creatinine
B-Leukocyte count	S/P-Bilirubin, total
B-Absolute neutrophil count	S/P-Alkaline phosphatase (ALP)
B-Absolute lymphocyte count	S/P-Aspartate transaminase (AST)
B-Platelet count	S/P-Alanine transaminase (ALT)
B-Mean cell volume (MCV)	S/P-Albumin
	S/P-Potassium
	S/P-Calcium, total
Urinalysis (dipstick)	S/P-Sodium
	S/P- Urea or Blood Urea Nitrogen (BUN)
U-Hb/Erythrocytes/Blood	S/p- Total Protein
U-Protein/Albumin	
U-Glucose	

NB. In case a patient shows an AST **or** ALT $\geq 3 \times \text{ULN}$ together with total bilirubin $\geq 2 \times \text{ULN}$ please refer to Appendix A ‘Actions required in cases of increases in liver biochemistry and evaluation of Hy’s Law’, for further instructions.

6.3.1.1 Coagulation

- activated partial thromboplastin time (APTT) will be performed at screening and if clinically indicated
- international normalized ratio ²⁰ will be performed at screening and if clinically indicated. Patients taking warfarin may participate in this study; however, it is recommended that INR be monitored carefully at least once per week for the first month, then monthly if the INR is stable.

Each coagulation test result will be recorded in CRF.

6.3.1.2 Bone marrow or blood cytogenetic samples

Bone marrow or blood cytogenetic samples may be collected for patients with prolonged hematological toxicities as defined in Section 6.5.5.1

Bone marrow analysis should include an aspirate for cellular morphology, cytogenetic analysis and flow cytometry, and a core biopsy for bone marrow cellularity. If it is not possible to conduct cytogenetic analysis or flow cytometry on the bone marrow aspirate, then attempts should be made to carry out the tests on a blood sample. Full reports must be provided by the investigator for documentation on the Patient Safety database. These data are not required to be entered into CRF.

6.3.2 Physical examinations

Physical examinations will be performed according to the assessment schedules (see the SoA). Full physical examinations will include assessments of the head, eyes, ears, nose, and throat, and the respiratory, cardiovascular, GI, musculoskeletal, neurological, and dermatological systems. Height will be measured at screening only. Focused physical examinations are to be utilized by the treating physician on the basis of clinical observations and symptomatology. Situations in which physical examination results should be reported as AEs are described in section 6.4.7.

6.3.3 Vital signs

Vital signs (blood pressure [BP], pulse, temperature, and respiration rate) will be evaluated according to the SoA. Body weight is also recorded at each visit along with vital signs.

6.3.4 Electrocardiograms

Resting 12-lead ECGs will be recorded at screening and as clinically indicated throughout the study. ECGs should be obtained after the patient has been in a supine position for 5 minutes and recorded while the patient remains in that position.

In case of clinically significant ECG abnormalities, 2 additional 12-lead ECGs should be obtained over a brief period (e.g., 30 minutes) to confirm the finding

6.4 Data Monitoring and Collection of Adverse Events

The Principal Investigator is responsible for ensuring that all staff involved in the study are familiar with the content of this section.

Trial monitoring will be in accordance with the Fred Hutchinson Cancer Research Center (FHCRC)/University of Washington Cancer Consortium Institutional Data and Safety Monitoring Plan. Under the provisions of this plan, FHCRC Clinical Research Support coordinates data and compliance monitoring conducted by consultants, contract research organizations, or FHCRC employees unaffiliated with the conduct of the study. Independent monitoring visits occur at specified intervals determined by the assessed risk level of the study and the findings of previous visits per the institutional DSMP.

In addition, protocols are reviewed at least annually and as needed by the Consortium Data and Safety Monitoring Committee (DSMC), FHCRC Scientific Review Committee (SRC) and the FHCRC/University of Washington Cancer Consortium Institutional Review Board (IRB). The review committees evaluate accrual, adverse events, stopping rules, and adherence to the applicable data and safety monitoring plan for studies actively enrolling or treating patients. The IRB reviews the study progress and safety information to assess continued acceptability of the risk-benefit ratio for human subjects. Approval of committees as applicable is necessary to continue the study.

The trial will comply with the standard guidelines set forth by these regulatory committees and other institutional, state and federal guidelines.

Additionally, scheduled meetings will take place weekly and will include the Sponsor Investigator ([name]), research nurse, data manager, and, when appropriate, the collaborators, sub-investigators, and biostatistician involved with the conduct of the protocol. During these meetings the Sub-Investigators/ Sponsor Investigator will discuss matters related to: safety of protocol participants, validity and integrity of the data, enrollment rate relative to expectation, characteristics of participants, retention of participants, adherence to protocol (potential or real protocol violations), data completeness, and progress of data for secondary objective.

AE will be reported by the patient (or, when appropriate, by a caregiver, surrogate, or the patient's legally authorized representative).

The investigator and any designees are responsible for detecting, documenting, and recording events that meet the definition of an AE or SAE. For information on how to follow/up AEs see section 8.3.3.

6.4.1 Method of detecting AEs and SAEs

Care will be taken not to introduce bias when detecting AEs and/or SAEs. Open-ended and non-leading verbal questioning of the patient is the preferred method to inquire about AE occurrences.

6.4.2 Time period and frequency for collecting AE and SAE information

Adverse Events will be collected from time of enrolment throughout the treatment period and including the follow-up period until last contact.

SAEs will be recorded from the time of signing of informed consent form.

All SAEs will be recorded and reported to the sponsor or designee within 24 hours, as indicated in Appendix B. The investigator will submit any updated SAE data to the sponsor within 24 hours of it being available.

Investigators are not obligated to actively seek AE or SAE in former study patients. However, if the investigator learns of any SAE, including a death, at any time after a patient's last visit and he/she considers the event to be reasonably related to the Study treatment or study participation, the investigator may notify the sponsor.

The method of recording, evaluating, and assessing causality of AE and SAE and the procedures for completing and transmitting SAE reports are provided in Appendix B.

6.4.2.1 Adverse events after the end of treatment visit

For Pharmacovigilance purposes and characterization, any SAE of MDS/AML or new primary malignancy occurring after end of treatment should be reported to AstraZeneca Patient Safety regardless of investigator's assessment of causality or knowledge of the treatment arm. Investigators will be asked during the regular follow up for overall survival if the patient has developed MDS/AML or a new primary malignancy and prompted to report any such cases.

At any time after a patient has completed the study, if an Investigator learns of any SAE including sudden death of unknown cause, and he/she considers there is a reasonable possibility that the event is causally related to the investigational product, the investigator should notify AstraZeneca, Patient Safety.

If patients who are gaining clinical benefit are allowed to continue study treatment post data cut off and/or post study completion then all SAEs must continue to be collected and reported to Patient Safety within the usual timeframe.

Otherwise, after study treatment completion (i.e. after any scheduled post treatment follow-up period has ended) there is no obligation to actively report information on new AEs or SAEs occurring in former study patients. This includes new AEs/SAEs in patients still being followed up for survival but who have completed their end of treatment visit.

6.4.3 Follow-up of AEs and SAEs

After the initial AE/SAE report, the investigator is required to proactively follow each patient at subsequent visits/contacts. All AEs/non-serious AEs/AEs of special interest (as defined in Section 6.4.13, will be followed until resolution, stabilization, the event is otherwise explained, or the patient is lost to follow-up

Any AEs that are unresolved at the patient's last AE assessment or other assessment/visit as appropriate in the study are followed up by the Investigator for as long as medically indicated, but without further recording in the CRF. AstraZeneca retains the right to request additional information for any patient with ongoing AE(s)/SAE(s) at the end of the study, if judged necessary.

Any SAE or non-serious adverse event that is ongoing at the time of the end of treatment visit, must be followed up to resolution unless the event is considered by the investigator to be unlikely to resolve, or the patient is lost to follow up. AstraZeneca retains the right to request additional information for any patient with ongoing AE(s)/SAE(s) at the end of the study, if judged necessary

6.4.4 Adverse event data collection

'The following variables will be collect for each AE;

- AE (verbatim)
- The date when the AE started and stopped
- CTCAE grade and changes in CTCAE grade
- Whether the AE is serious or not
- Investigator causality rating against the Investigational Product(s) (yes or no)
- Action taken with regard to Investigational Product(s)
- AE caused subject's withdrawal from study (yes or no)
- Outcome.

In addition, the following variables will be collected for SAEs:

- Date AE met criteria for serious AE
- Date Investigator became aware of serious AE
- AE is serious due to
- Date of hospitalization
- Date of discharge
- Probable cause of death
- Date of death
- Autopsy performed
- Causality assessment in relation to Study procedure(s)
- Causality assessment to other medication'

- Description of AE

6.4.5 Causality collection

The Investigator will assess causal relationship between Investigational Product and each Adverse Event, and answer ‘yes’ or ‘no’ to the question ‘Do you consider that there is a reasonable possibility that the event may have been caused by the investigational product?’

For SAEs, causal relationship will also be assessed for other medication and study procedures . Note that for SAEs that could be associated with any study procedure the causal relationship is implied as ‘yes’.

A guide to the interpretation of the causality question is found in Appendix B to the Clinical Study Protocol.

6.4.6 Adverse events based on signs and symptoms

All AEs spontaneously reported by the patient or care provider or reported in response to the open question from the study site staff: “Have you had any health problems since the previous visit/you were last asked?”, or revealed by observation will be collected and recorded in the CRF. When collecting AEs, the recording of diagnoses is preferred (when possible) to recording a list of signs and symptoms. However, if a diagnosis is known and there are other signs or symptoms that are not generally part of the diagnosis, the diagnosis and each sign or symptom will be recorded separately.

6.4.7 Adverse events based on examinations and tests

The results from the Clinical Study Protocol mandated laboratory tests and vital signs will be summarized in the CSR. Deterioration as compared to baseline in protocol-mandated laboratory values and vital signs should therefore only be reported as AEs if they fulfil any of the SAE criteria or are the reason for discontinuation of treatment with the investigational product.

If deterioration in a laboratory value/vital sign is associated with clinical signs and symptoms, the sign or symptom will be reported as an AE and the associated laboratory result/vital sign will be considered as additional information. Wherever possible the reporting Investigator uses the clinical, rather than the laboratory term (e.g., anemia versus low hemoglobin value). In the absence of clinical signs or symptoms, clinically relevant deteriorations in non-mandated parameters should be reported as AE(s).

Deterioration of a laboratory value, which is unequivocally due to disease progression, should not be reported as an AE/SAE.

Any new or aggravated clinically relevant abnormal medical finding at a physical examination as compared with the baseline assessment will be reported as an AE unless unequivocally related to the disease under study.

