6.5.5.1 Management of hematological toxicity

Management of anemia

Table 10 Management of anemia

Hemoglobin	Action to be taken
Hb < 10 but \geq 8 g/dl (CTCAE Grade 2)	First occurrence: Give appropriate supportive treatment and investigate causality. Investigator judgement to continue olaparib with supportive treatment (eg transfusion) or interrupt dose for a maximum of 4 weeks. Study treatment can be restarted if Hb has recovered to > 9 g/dl. Subsequent occurrences: If Hb < 10 but \geq 9 g/dl investigator judgement to continue olaparib with supportive treatment (eg. transfusion) or dose interrupt (for max of 4 weeks) and upon recovery dose reduction may be considered (to 250 mg twice daily as a first step and to 200 mg twice daily as a second step). If Hb < 9 but \geq 8 g/dl, dose interrupt (for max of 4 weeks) until Hb \geq 9 g/dl and upon recovery dose reduction may be considered (to 250 mg twice daily as a first step and to 200 mg twice daily as a second step).

Hemoglobin	Action to be taken
Hb < 8 g/dl (CTCAE Grade 3)	Give appropriate supportive treatment (e.g. transfusion) and investigate causality. Interrupt olaparib for a maximum of 4 weeks until improved to Hb \geq 9 g/dl. Upon recovery dose reduce to 250 mg twice daily as a first step and to 200 mg twice daily as a second step in the case of repeat Hb decrease.

Common treatable causes of anemia (e.g., iron, vitamin B12 or folate deficiencies and hypothyroidism) should be investigated and appropriately managed. In some cases, management of anemia may require blood transfusions. For cases where patients develop prolonged hematological toxicity (\geq 2 week interruption/delay in study treatment due to CTC grade 3 or worse anemia and/or development of blood transfusion dependence), refer to guidance later in this section for the management of this.

Management of neutropenia, leukopenia and thrombocytopenia

Table 11 Management of neutropenia, leukopenia and thrombocytopenia

Toxicity	Study treatment dose adjustment
CTCAE Grade 1-2	Investigator judgement to continue treatment or if dose interruption, this should be for a maximum of 4 weeks; appropriate supportive treatment and causality investigation
CTCAE Grade 3-4	Dose interruption until recovered to CTCAE gr 1 or better for a maximum of 4 weeks. If repeat CTCAE grade 3-4 occurrence, dose reduce olaparib to 250 mg twice daily as a first step and 200 mg twice daily as a second step

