6.9.2 Safety analyses

All patients who initiate study treatment will be evaluated for safety, combined across both cohorts. Adverse events will be summarized as number (%) of patients by system organ class, CTCA term and grade, where grade is the maximum across a patient's treatment period.

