Appendix B Adverse event definitions and additional safety information

B 1 Definition of adverse events

An adverse event is the development of any untoward medical occurrence in a patient or clinical study patient administered a medicinal product and which does not necessarily have a causal relationship with this treatment. An AE can therefore be any unfavourable and unintended sign (e.g. an abnormal laboratory finding), symptom (for example nausea, chest pain), or disease temporally associated with the use of a medicinal product, whether or not considered related to the medicinal product.

The term AE is used to include both serious and non-serious AEs and can include a deterioration of a pre-existing medical occurrence. An AE may occur at any time, including run-in or washout periods, even if no Study treatment has been administered.

B 2 Definitions of serious adverse event

A serious adverse event is an AE occurring during any study phase (i.e., run-in, treatment, washout, follow-up), that fulfils one or more of the following criteria:

- Results in death
- Is immediately life-threatening
- Requires in-patient hospitalization or prolongation of existing hospitalization
- Results in persistent or significant disability or incapacity.
- Is a congenital abnormality or birth defect
- Is an important medical event that may jeopardize the patient or may require medical treatment to prevent one of the outcomes listed above.

B 3 Life threatening

‘Life-threatening’ means that the patient was at immediate risk of death from the AE as it occurred or it is suspected that use or continued use of the product would result in the patient’s death. ‘Life-threatening’ does not mean that had an AE occurred in a more severe form it might have caused death (e.g., hepatitis that resolved without hepatic failure).

B 4 Hospitalization

Outpatient treatment in an emergency room is not in itself a serious AE, although the reasons for it may be (e.g., bronchospasm, laryngeal oedema). Hospital admissions and/or surgical operations planned before or during a study are not considered AEs if the illness or disease existed before the patient was enrolled in the study, provided that it did not deteriorate in an unexpected way during the study.

B 5 Important medical event or medical treatment

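### Read literally, section 6.4.7 leaves non-serious, asymptomatic grade 3–4 cytopenias managed by a hold or dose reduction out of the CTCAE adverse event endpoint

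*Combined protocol and SAP*

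**What the plan says.** Section 6.4.7 sets the reporting rule. Deteriorations in protocol-mandated laboratory values "should therefore only be reported as AEs if they fulfil any of the SAE criteria or are the reason for discontinuation" of the investigational product. The reason given is that "The results from the Clinical Study Protocol mandated laboratory tests and vital signs will be summarized in the CSR". Two further provisions follow. Where a laboratory change comes with symptoms, "the sign or symptom will be reported as an AE and the associated laboratory result/vital sign will be considered as additional information". For changes without symptoms, the only provision is: "In the absence of clinical signs or symptoms, clinically relevant deteriorations in non-mandated parameters should be reported as AE(s").

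Blood counts are mandated. Section 6.3.1 states that "Blood samples for determination of clinical chemistry and hematology will be taken at the times indicated in the assessment schedules", Table 9 lists hemoglobin, leukocytes, neutrophils and platelets, and the Schedule of Activities has a CBC with differential every cycle.

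Section 6.5.5.1 ties dosing to the laboratory value. For grade 3–4 neutropenia, leukopenia or thrombocytopenia, Table 11 has "Dose interruption until recovered to CTCAE gr 1 or better for a maximum of 4 weeks", and a dose reduction if it recurs. Table 10 requires interruption for hemoglobin below 8 g/dl and a reduction on recovery.

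The secondary safety endpoint (sections 3.2 and 3.5) is incidence and severity of AEs by CTCAE. The planned analysis in section 6.9.2 is: "Adverse events will be summarized as number (%) of patients by system organ class", then by CTCAE term and maximum grade. It names no laboratory grading, shift table or dose-modification summary.

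**The concern.** Whether a laboratory change counts as an AE depends on seriousness or permanent stopping, while the dosing rules and the safety endpoint both work by CTCAE grade. An event severe enough to force a hold or a lower dose can therefore fall outside the table that is meant to describe incidence and severity.

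Hematologic toxicity is among the known olaparib risks in section 2.2, so this is a toxicity the endpoint should be able to show. Section 6.4.4 collects CTCAE grade, causality and action taken with study drug for each AE, so an event not reported as an AE has none of these on an AE form. Section 6.4 has the review committees evaluate adverse events, so they would see the same incomplete count.

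**Working it through.** There is no stated figure in the plan to reproduce. The check is textual, followed by an illustration on assumed rates.

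**Step 1. Routes into the AE table for a blood count under 6.4.7**

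1. It meets an SAE criterion (Appendix B 2, including important medical events).
2. It is the reason for discontinuing olaparib.
3. It is associated with signs or symptoms; the symptom is then the AE.
4. It is a non-mandated parameter. This route is closed, because blood counts are mandated.

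No route is triggered by CTCAE grade, by a hold or by a dose reduction.

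**Step 2. Typical cases put through those routes**

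| Case | Dosing consequence in 6.5.5.1 | AE under 6.4.7, read literally? |
|---|---|---|
| Grade 3–4 neutropenia or thrombocytopenia, no symptoms, recovers within 4 weeks | Interruption | No, unless judged serious |
| The same, recurring | Dose reduction | No, unless judged serious |
| Hemoglobin below 8 g/dl, no symptoms, not transfused | Interruption, then reduction | No, unless judged serious |
| Hemoglobin below 8 g/dl, transfused | Interruption, then reduction | Possibly, as an important medical event (Appendix B 5) |
| Cytopenia not recovered to grade 1 after 4 weeks | Discontinuation | Yes, by route 2 |
| Cytopenia with symptoms | As for its grade | The symptom is reported; the count is supporting information |

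The gap is the first three rows: non-serious, asymptomatic and followed by resumed treatment.

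**Step 3. Illustration of size**

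Inputs: N = 30 planned patients (section 6.8). Section 6.9.2 includes everyone who starts treatment. Let p be the share of men with a grade 3–4 laboratory cytopenia, and f the share of those men who are non-serious, asymptomatic and do not discontinue. The documents give neither, so both are assumed and varied.

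Men affected = 30 × p. Share shown in the AE table = p × (1 − f).

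| p | Men affected | f = 0.25 | f = 0.50 | f = 0.75 | f = 1 |
|---|---|---|---|---|---|
| 5% | 1.5 | 3.75% | 2.5% | 1.25% | 0% |
| 10% | 3 | 7.5% | 5% | 2.5% | 0% |
| 20% | 6 | 15% | 10% | 5% | 0% |
| 30% | 9 | 22.5% | 15% | 7.5% | 0% |

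At f = 0.50, a true 5–30% would appear as 2.5–15%. For example, at p = 20%, 30 × 0.20 = 6 men have the event and 6 × 0.50 = 3 are tabulated.

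**The case against.** The case for leaving the plan alone has real content.

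- **Seriousness route.** Appendix B 5 gives blood dyscrasias, with transfusion-requiring anemia as an example, among important medical events. Table 10 names transfusion as an example of supportive treatment for hemoglobin below 8 g/dl, so a good share of grade 3 anemias could enter this way. This stands, but it depends on case-by-case judgement and does little for an asymptomatic neutropenia or thrombocytopenia managed by a hold.
- **Other sections already call these events AEs.** Tables 10 and 11 sit under the AE-management section (6.5.5). Section 6.5.5.1 refers to neutropenia and leukopenia as adverse events, and section 5.11 includes long holds attributed to an AE among its reasons for stopping. Table 5 also uses the language of discontinuation for a temporary stop before radiotherapy. A site could reasonably report a cytopenia that causes a hold. This stands too, and it makes the practical result inconsistent reporting rather than certain omission.
- **The data are kept.** Laboratory results are promised for the study report, and section 6.5.5.2 puts reductions, interruptions and their reasons in the eCRF. This is correct. A reader might infer that dose changes would go unexplained or that the events are lost; neither follows. But the promised laboratory summary has no specified content and is not part of the CTCAE endpoint.
- **Definition versus reporting rule.** Appendix B 1 says: "An AE can therefore be any unfavourable and unintended sign (e.g. an abnormal laboratory finding"). A reader might call this a flat contradiction of 6.4.7. It is not: B 1 says what an AE can be, while 6.4.7 narrows what is reported and gives a reason. The two are in tension, and the plan does not say which governs.
- **Limited reach.** The endpoint is descriptive and secondary, the drug is given at its approved dose, and the PSA50 analysis is untouched. This limits the importance of the point but does not answer it.

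**Conclusion.** The point holds in limited form. Followed as written, 6.4.7 together with 6.9.2 leaves non-serious, asymptomatic grade 3–4 cytopenias out of the CTCAE AE table when they are managed by a hold or reduction, even though Tables 10 and 11 act on the grade alone. The rule can only lower the tabulated incidence, so the table may understate hematologic toxicity. Whether it does depends on how sites read the competing sections and how often Appendix B 5 is applied.

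The size is unknown. The 2.5–15% against a true 5–30% rests on two assumptions: the event rate, and that half of the affected men fall in the gap. A reader might take one cell of that grid as an estimate; nothing in the documents supports any particular cell. Nor do they show that cytopenia is the drug's leading toxicity, since section 2.2 lists hematologic effects first without ranking them. The argument does not extend to creatinine or liver tests; combined liver elevations have their own route in section 6.4.8 and Appendix A.

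**What to change.** The changes concern reporting and analysis only and alter no dosing or management rule.

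1. In 6.4.7, state that a laboratory deterioration of CTCAE grade 3 or higher, or one that leads to dose interruption, dose reduction, transfusion or growth factor use, is recorded as an AE. This reconciles the section with 5.11, 6.5.5, 6.5.5.1 and Appendix B 1 and B 5, and gives sites a single rule.
2. In 6.9.2, add a table of worst on-treatment CTCAE grade and shift from baseline for hemoglobin, neutrophils, leukocytes and platelets, with counts of holds and reductions by cause.

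The cost is wording in two sections and one added analysis from the CBC and eCRF data already collected. The downside is more AE forms for sites and a less favourable AE count.
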